3.2 Secondary Objective

The secondary objective is to assess the differences between both Sites in change in size of keloids post treatment.

3.3 Exploratory objective

The exploratory objective is to assess the differences between both Sites in patients subjective experiences, such as pain related to treatment, healing time.

CONFIDENTIAL

This material is the property of the NYU School of Medicine and Langone Medical Center. Do not disclose or use except as authorized in writing by the study sponsor
Interventional Template Version: 11 January 2019

4 Study Design and Endpoints

In light of the COVID-19 pandemic, the study team will utilize a verbal recruitment template and COVID19 information sheet to make patients aware of risks of completing an in-person research study. The study team and patients will be protected by complying with all NYU safety measures, including screening, social distancing, PPE, cleaning/disinfecting.

Daily symptoms screening for research personnel

- Each faculty member, employee, and student will complete a "Daily Symptom Check" one to three hours ahead of the start of their time as part of the research study.

Screening research participants for symptoms

- The study team will be responsible for screening research participants in alignment with clinical screening of patients: upon scheduling, appointment reminders, and arrival at the research location.
- Patients will be asked 1. Do you have two or more Covid-19-like symptoms (cough, shortness of breath, fever, chills, shaking chills, muscle pain, headache, sore throat, new loss of taste or smell)? 2. Have you or anyone in household tested positive in the last 10 days? If either question is answered yes, the participant cannot come to their in-person appointment.
- During the screening process study teams must notify research participants that they are required to wear a mask/face covering.
- Upon arrival to NYULH locations, research participants are subject to the same screening procedures as patients.

Social distancing

- Office visits will be staggered to minimize number of individuals in waiting areas
- Waiting rooms/public areas will have seats spread to 6 feet of separation
- The number of study personnel in exam rooms will be minimized

Personal Protective Equipment for research personnel

- All NYU Langone staff, faculty, students, and trainees will wear a face mask at all times
- Researchers will also follow any additional PPE guidelines for our clinical area
- Masks will be worn in all public and work spaces and patient care areas, worn correctly to cover the mouth and nose

CONFIDENTIAL

- Only NYU Langone-issued masks or personal protective equipment will be worn, no cloth masks or non-NYU Langone issued masks or PPE will be utilized

Personal Protective Equipment for research participants

- All participants and visitors >4 years of age will be offered a face mask upon entry to the ambulatory site
- Patients will be informed to arrive with a face mask during the pre-visit phone call
- Masks will be worn throughout participant's appointments

Cleansing and disinfecting

- All personnel will wash hands or use hand sanitizer often, especially when entering work areas from public spaces and after contacting high-touch surfaces like doorknobs and handles, refrigerator and freezer handles, and elevator buttons

4.2 Study Endpoints

4.2.1 Primary Study Endpoints

We will measure the non-blinded POSAS score at every visit. The POSAS was created in 2004 and takes both the patient and the provider perspectives into account. The POSAS scar scale has been found to be more reliable and less variable than other scar scales utilized in clinical practice⁴³.

POSAS has two components, the observer (physician) portion and the patient portion. The observer grades on a scale of 1 to 10, 10 being the worst scar imaginable, six measures: vascularity, pigmentation, thickness, relief, pliability and surface area. The patient answers six questions regarding the characteristics of the scar, with each question being on a scale of 1 to 10. The scores of each category are summed to get the total POSAS score, with 120 being the highest score and representing the worst scar.

1. The first primary endpoint is the POSAS score in Site A and Site B at first visit (pre-treatment) and last visit (post-treatment).
2. The second primary endpoint is a modified Hamilton score based on comparing clinical photographs of the scarred skin and healthy skin next to each other in Site A and Site B.

4.2.2 Secondary Study Endpoint

The secondary endpoint is measurements of the scar in both Sites of the keloid. The measurements will be calculated as the total volume (length x width x height) in cm³ of the scar, or length x width in cm² if the scars are flush with the surrounding skin scar surface in the two Sites of the keloid.

4.2.3 Exploratory Endpoints

Patient's subjective experiences measured as follows:

1. Patient perceived side effects after each treatment at visits 1, 2, 3, and 4 in Site A and Site B, in terms of dyspigmentation, pain, itch, swelling.
2. Pain grade after each laser treatment at visits 1, 2, 3, and 4, measured on a scale of 1 to 10 (10 being the worst pain), in Site A and Site B, recorded at the subsequent follow up visit.
3. Perceived speed of healing at final visit (visit 5) will be compared between both Sites using the following answers: Site A healed faster than Site B, Site B healed faster than Site A, Same speed of healing in both Sites

CONFIDENTIAL

This material is the property of the NYU School of Medicine and Langone Medical Center. Do not disclose or use except as authorized in writing by the study sponsor
Interventional Template Version: 11 January 2019

5 Study Enrollment and Withdrawal

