2.2.1 Clinical Data to Date

In 2013, Waibel *et al.* used ablative fractional photo-thermolysis CO₂ laser treatments to aid corticosteroid delivery in hypertrophic scars. Three to five laser treatments at 2-month to 3-month intervals were combined with a thin topical layer of TAC suspension of 10 or 20 mg/mL, depending on the location and thickness of the skin. They observed an overall scar improvement, with the therapy having the greatest impact on texture but also improved dyschromia and overall appearance.⁸

Park *et al.* compared laser-assisted topical corticosteroid with intralesional corticosteroid injections in keloids. First, the entire keloid was treated with fractional ablative Er:YAG laser. The lesions were subsequently divided into two halves, with the first half receiving intralesional TAC injection (10 mg/mL) and the second receiving topical application of desoxymethasone 0.25% ointment. Four treatments at 6-week

CONFIDENTIAL

This material is the property of the NYU School of Medicine and Langone Medical Center. Do not disclose or use except as authorized in writing by the study sponsor
Interventional Template Version: 11 January 2019

intervals were conducted. They found a statistically significant improvement in the Vancouver Scar Scale (VSS) for both modalities, but the corticosteroid injection was associated with much more severe pain.¹²

In 2019, Waibel *et al.* compared clinical outcomes of hypertrophic scars treated with laser-assisted corticosteroid delivery versus laser-assisted 5-FU delivery. Subjects underwent 3 treatment sessions at 1-month intervals consisting of fractional ablative CO₂ laser treatment followed by postoperative application of either TAC solution (20 mg/mL) or 5-FU solution (50 mg/mL). Scars treated with both modalities demonstrated reduction in overall scar surface area. There was no statistically significant difference between the arms, suggesting that neither agent possesses superior efficacy over the other. However, 5-FU was not associated with the side effect risks that topical corticosteroids foster such as dermal atrophy or telangiectasia formation.¹

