2.3 Rationale

The primary objective of this study is to determine the differences in clinical outcome and side effect profile for keloids treated with laser-assisted 5-FU delivery as compared to laser-assisted corticosteroid delivery. Transdermal delivery of drugs is limited by permeation through the stratum corneum, where high-molecular weight and hydrophilic compounds often cannot penetrate.²⁹⁻³¹ Topical medications have been found to have a total absorption with only 1% to 5% bioavailability of the applied dose. Intralesional injection requires multiple needle punctures, which can be difficult to tolerate. Laser-assisted drug delivery can improve cutaneous penetration while being less painful.¹²

We hypothesize that efficacy is greater in keloids treated with laser-assisted delivery of 5-FU as compared to those treated with laser-assisted delivery of TAC 10mg/mL, and we expect to see less adverse effects such as hypopigmentation with 5-FU.

Er:YAG laser operates at a wavelength of 2940 nm and is an ablative laser as its energy is highly absorbed by water-containing tissue.^{9,32} Er:YAG has been shown to enhance permeation of 5-FU by 53-fold to 133-fold in mouse models.³³ Er:YAG has also been shown to increase the penetration of lipophilic and hydrophilic compounds through the skin.³⁴ Er:YAG laser has demonstrated safety as a transdermal transport enhancer, with studies showing the depths of the stratum corneum and epidermis recovering to normal conditions within 3-5 days.^{33,34} Once the stratum corneum and epidermis are surpassed, the depth of the ablation does not affect drug delivery.^{35,36} Of importance in our study, fractional Er:YAG laser is associated with decreased risk of post-inflammatory hyperpigmentation (PIH) as compared to CO₂ laser.^{37,38} Skin of color (Fitzpatrick skin types IV, V, VI) is more prone to developing keloids and has a generally increased risk of PIH compared to lighter skin types. As such, the fractional erbium laser is the safer choice for our target population.

5-FU will be used at the dose of 50 mg/mL and TAC will be used at the dose of 10mg/mL; the amount will depend on the size of the keloid treated.

CONFIDENTIAL

This material is the property of the NYU School of Medicine and Langone Medical Center. Do not disclose or use except as authorized in writing by the study sponsor

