2.4 Potential Risks & Benefits

2.4.1 Known Potential Risks

Known potential risks of laser treatment include pain, bleeding and swelling. Known potential risks of laser-assisted delivery of each medication is no different than the potential risks of injecting each medication intradermally. There is no known risk of cross-reaction if both 5-FU and TAC are injected in the same scar; in fact, both have been mixed and injected into keloids at the same for enhanced clinical efficacy.¹⁶ Keloids treated with erbium laser have been shown to have a good safety profile.^{37,39} As aforementioned, 5-FU can be applied on open wounds for actinic keratoses as approved by the FDA (sometimes followed by TAC in case of brisk reaction) or even given intravenously in even higher doses for GI malignancies.^{40,41}

TAC is used to treat a wide variety of dermatologic conditions (including open wounds/ulcers like pyoderma gangrenosum) and is the prototypical corticosteroid used to treat pathological scarring.⁴² Topical side effects include dermal atrophy, fat atrophy, erythema, telangiectasias, hypopigmentation, hyperpigmentation, scarring, easy bruising, and certain inflammatory skin conditions.^{8,29}

5-FU is an anti-metabolite widely used in cancer chemotherapy, both intravenously (FOLFOX in gastrointestinal malignancies) and topically.⁴⁰ Sabry *et al.* found that topical application of 5-FU after laser sessions showed no side effects, though others report topical side effects of 5-FU include local pain, dermatitis, pruritus, burning, photosensitivity, pigmentation changes, and scarring.^{25,29} A review of intralesional injections of 5-FU found negative side effects that may include pain at the injection site, ulceration, burning, and hyperpigmentation; no systemic complications such as anemia, leukopenia, and thrombocytopenia were reported.³⁷

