7.2.1 Treatment Visits

Visits 1 - 4

- Urine pregnancy test if female of child-bearing age. (visits 2-4)
- Physical examination of lesion of interest.
- Photography of lesion (keloid) of interest, taken before any treatment is performed
- Measurement (height, length, width) of lesion (keloid) of interest performed at the start of the visit, before treatment
- Completion of POSAS (including monitoring of adverse events) by patient and providers at the start of the visit
- Administer the study treatment (to be performed by PI): laser assisted drug-delivery treatment of both 5-FU and TAC.
- Monitoring of adverse events
- Patients will be asked about side effects (non-serious adverse events) from laser treatment on visits 2-4
- Patients will be asked to grade their post-procedure pain on a scale of 1 to 10 on visits 2-4
- Patients will be asked which side healed faster after the laser treatment on visits 2-4
- Post-treatment instructions will be provided to patients on an after-treatment instruction sheet: gentle cleansing of area with soap and water twice a day, apply petrolatum jelly and keep area covered for 1 week, avoid sun exposure to treated area(s) for study duration.
- Visits will take place every 4 weeks ± 1 week.

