10.2.5 Exploratory Analysis

Patient's subjective experiences will be summarized and compared between both Sites of the keloid as follows:

CONFIDENTIAL

This material is the property of the NYU School of Medicine and Langone Medical Center. Do not disclose or use except as authorized in writing by the study sponsor
Interventional Template Version: 11 January 2019

1. Patient perceived side effects after each treatment will be summarized by type (dyspigmentation, pain, itch, swelling), visit (1, 2, 3, 4) and treatment Site (A, B).
2. Pain after each laser treatment will be summarized by grade (scale of 1 to 10 (10 being the worst pain)), visit (1, 2, 3, 4) and treatment Site (A, B).
3. Speed of healing after completion of laser treatments at final visit (visit 5) will be compared between both Sites (Site A healed faster than Site B, Site B healed faster than Site A, Same speed of healing in both Sites)

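### The only planned by-Site side-effect summary pools hypo- and hyperpigmentation and omits atrophy, telangiectasia and ulceration, so no planned analysis isolates the effect that section 2.3 predicts

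*Combined protocol and SAP*

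**What the plan says.** Section 2.3 states that the study will "determine the differences in clinical outcome and side effect profile for keloids treated with laser-assisted 5-FU delivery" as compared with laser-assisted corticosteroid, and that "we expect to see less adverse effects such as hypopigmentation with 5-FU". Section 3.1, the formal list of primary objectives, covers POSAS and the modified Hamilton score only.

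The risk text is more detailed than the endpoint:
- Section 2.2.1, on the earlier head-to-head study in hypertrophic scars: "5-FU was not associated with the side effect risks that topical corticosteroids foster such as dermal atrophy or telangiectasia formation".
- Section 2.4.1 lists dermal and fat atrophy, telangiectasias, and both hypo- and hyperpigmentation for TAC. For intralesional 5-FU it lists "pain at the injection site, ulceration, burning, and hyperpigmentation". For topical 5-FU it lists pigment change without direction.
- Section 2.2.2 justifies the TAC strength partly by the risk of dyspigmentation and atrophy at higher doses.

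The by-Site endpoint in 4.2.3 records patient-perceived effects "in terms of dyspigmentation, pain, itch, swelling". Section 10.2.5 and the Protocol Summary repeat these four types, to be summarized by visit and Site. The lead-in to 10.2.5 says the Sites will be compared, but no test or paired measure is named. Section 7.2.1 describes the question itself: "Patients will be asked about side effects (non-serious adverse events) from laser treatment on visits 2-4". Section 7.2.2 asks it again at Visit 5. Neither section lists types.

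**The concern.** The side-effect list does not match the protocol's own prediction or its own risk list. The effect that section 2.3 names is merged with its opposite. The two effects said to have separated the drugs in the earlier study have no place in the by-Site summary. At the end, the trial could report how often participants noticed some pigment change at each Site without being able to say whether 5-FU produced less hypopigmentation, or whether atrophy differed between the drugs. If direction is never asked, it may not be recoverable later.

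**Working it through.** **Step 1. Which planned record could isolate each effect, by Site and drug?**

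| Effect | Where the protocol raises it | By-Site item (4.2.3, 10.2.5) | Adverse event record (8.3) | POSAS observer part (4.2.1) |
|---|---|---|---|---|
| Hypopigmentation | 2.3 (predicted), 2.4.1 (TAC) | Pooled | Free description, Site not listed | Pigmentation 1 to 10, no stated direction |
| Hyperpigmentation | 2.4.1 (TAC, intralesional 5-FU) | Pooled | As above | As above |
| Atrophy | 2.2.1, 2.2.2, 2.4.1 (TAC) | Absent | As above | Thickness and relief, scored as scar quality |
| Telangiectasia | 2.2.1, 2.4.1 (TAC) | Absent | As above | Vascularity, scored as scar quality |
| Ulceration | 2.4.1 (intralesional 5-FU) | Absent | As above | None |

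The fields listed in 8.3 are description, onset, severity, relationship and resolution. Each participant receives both drugs, so an event without a Site need not be attributable to one of them. Section 10 has no adverse event analysis by Site or drug, and its POSAS test does not use single items. Site A and Site B are anatomical labels in 4.1, with the drug for Site A randomized. A summary by Site becomes a summary by drug only after the allocation is applied.

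**Step 2. The plan's own figures.** The only power table (10.1) concerns POSAS. It uses SD = 27 × √(2(1−r)) × √(2(1−r)) = 54(1−r), so r = 0.5 gives 27.0. With the Wilcoxon efficiency 3/π and N = 20, the detectable means come out at 32.94, 27.45, 18.30, 9.15 and 3.66, against 33.0, 27.5, 18.4, 9.2 and 3.7 in the table. The table reproduces but says nothing about side effects.

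**Step 3. What pooling can do.** The documents give no side-effect rates, so every rate below is an assumption. The test is also only a yardstick, because the plan names none: exact two-sided McNemar, 20 participants, alpha 0.05, Sites independent. With p_T and p_F the proportions affected on TAC and 5-FU, the discordant probabilities are p_T(1−p_F) and p_F(1−p_T). Power is the multinomial probability of all discordant counts (i, j) with 2 × P(Bin(i+j, 0.5) ≤ min(i, j)) ≤ 0.05.

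Rows a to e assume that no Site shows both changes, so the rates add. Rows f to h assume that the two changes are independent: pooled = 1 − (1−hypo)(1−hyper). For row f, 1 − 0.60 × 0.90 = 46% on TAC and 1 − 0.95 × 0.65 = 38.25% on 5-FU.

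| Row | TAC hypo/hyper, % | 5-FU hypo/hyper, % | Hypo difference (power) | Pooled, % | Pooled difference (power) |
|---|---|---|---|---|---|
| a | 30/0 | 0/30 | 30 points (58%) | 30 vs 30 | 0 (2%) |
| b | 30/5 | 5/30 | 25 points (34%) | 35 vs 35 | 0 (2%) |
| c | 30/10 | 5/25 | 25 points (34%) | 40 vs 30 | 10 points (5%) |
| d | 40/5 | 5/20 | 35 points (64%) | 45 vs 25 | 20 points (16%) |
| e | 30/20 | 5/10 | 25 points (34%) | 50 vs 15 | 35 points (52%) |
| f | 40/10 | 5/35 | 35 points (64%) | 46 vs 38.25 | 7.75 points (4%) |
| g | 40/10 | 5/10 | 35 points (64%) | 46 vs 14.5 | 31.5 points (44%) |
| h | 40/40 | 5/40 | 35 points (64%) | 64 vs 43 | 21 points (16%) |

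Row e under independence gives 44% vs 14.5%, with power 39%.

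In rows a to d and f, hyperpigmentation is commoner on 5-FU and pooling hides the difference. In rows g and h it is equally common at both Sites, and pooling still dilutes it. In row e TAC causes more of both, and pooling enlarges it. Reporting hypopigmentation alone never exceeds 64% power in these rows.

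**The case against.** The strongest reply is that this is one exploratory, patient-perceived item with no power claim, and that other data exist. Section 8.3 captures all adverse events, local reactions included, with a description and relatedness, so atrophy or hypopigmentation can be written down. A blinded dermatologist grades each Site by POSAS at every visit, and photographs are taken at Visits 1 to 5. The prediction in 2.3 concerns adverse effects in general, with hypopigmentation as an example. All of this stands, and it limits the weight of the point. It does not supply a by-Site or by-drug analysis that isolates the named effect, and 4.1 leaves the treating physician unblinded to the adverse event assessment.

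A reader might infer three stronger things that the documents do not support:
- *The tolerability hypothesis cannot be tested at all.* Overall dyspigmentation can still be compared, and individual events can be described.
- *The two drugs cause opposite pigment harms that will cancel.* Section 2.4.1 lists both directions for TAC and gives no direction for topical 5-FU; the hyperpigmentation entry for 5-FU comes from a review of intralesional injection. No proportions are given. Cancellation is possible, but so is row e.
- *Existing keloid itch and pain will be counted as drug effects because the question starts at Visit 2.* Section 8.3 treats a condition present at screening as baseline unless it deteriorates, and 7.2.1 equates side effects with non-serious adverse events. The rule exists; it only needs to be tied explicitly to this item.

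**Conclusion.** The concern holds as a mismatch between the stated aim and the planned side-effect summary. Section 2.3 predicts less hypopigmentation with 5-FU, but no planned analysis separates hypopigmentation from hyperpigmentation, or compares atrophy, telangiectasia or ulceration between the drugs. This follows from the text alone.

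The numerical effect is unknown. Under the assumed rates, a true 25- to 35-point difference in hypopigmentation corresponds to a pooled difference anywhere from 0 to 35 points. That range rests on chosen rates, independent Sites and a test that the plan does not name, so it shows what is possible and not what to expect. Splitting the item would make the estimates interpretable; it would not make the hypothesis confirmable with 20 participants. Severity is minor.

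**What to change.** - In 4.2.3, 10.2.5 and the Protocol Summary, replace dyspigmentation with separate hypopigmentation and hyperpigmentation items for each Site. Sections 7.2.1 and 7.2.2 do not use the word and need no substitution.
- In 8.3, add Site (A or B) to the adverse event fields. Have atrophy, telangiectasia and ulceration recorded by Site by the clinician or, better for bias, by the blinded observer who already grades each Site. These are clinical signs and fit poorly in a patient-perceived item.
- State that the baseline rule in 8.3 applies to the side-effect items, with the Visit 1 pre-treatment assessment as the reference, so that only new or worsened effects count.
- In 10.2.5, specify a paired descriptive summary by drug (5-FU against TAC): for each effect, the number of participants with it on both Sites, on the 5-FU Site only, on the TAC Site only, and on neither.

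The cost is slightly longer forms at visits that already take place, some categories with few or no events, and estimates of limited precision at 20 participants, so the result stays descriptive. No treatment or visit changes.

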5.1 Inclusion Criteria

In order to be eligible to participate in this study, an individual must meet all of the following criteria:

1. Age 18-89
2. Has one large keloid scar or at least two similar but separate keloid scars
3. Keloid present for at least 1 year

